5.5 Recruitment / Enrollment Procedures

Eligible study patients will be identified at the participating centers by one of two ways. In some institutions, the echo database will be mined for all the normal echo studies that have been performed during the study period. The study coordinator will then review the charts of the patients to identify those who meet all inclusion criteria and do not have any of the exclusion criteria. At other centers, the hospital database will be mined for all healthy or normal patients meeting study criteria. The study coordinator will verify eligibility by reviewing the medical record and identifying the patients who have had an echo. The study coordinator will then review the echo reports to identify all those with a normal study. Other centers may use a combination of these two approaches. As discussed in Section 4.3, eligible study patients with acceptable echo images identified at centers that do not routinely collect race data will be contacted to obtain race and ethnicity data prospectively.

6. STATISTICS

6.1 Statistical Analysis Plan

BSA for each subject will be calculated using the Haycock formula (27). The distribution of BSA and each echo measurement will be assessed and tested for normality. Any variable found to be skewed or otherwise non-normal will be transformed appropriately in order to obtain a normal (or close to normal) distribution. The analysis will require classification of each subject within one of 36 study groups based on:

- 6 age categories
 - <1 month old
 - 1 month old – <3 years old
 - 3 – <6 years old
 - 6 – <12 years old
 - 12 – <16 years old
 - 16 – 18 years old

- 2 gender categories
 - Male
 - Female
- 3 race categories
 - White
 - African-American
 - Other

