6.1.1 Derivation of Mean and Standard Deviation

The mean and SD of a given measurement will be derived for each of the 36 study groups described above. For a given group, the mean (E) and SD of an echo measurement (Y), given the BSA, are as follows:

$$E(Y|BSA) = \mu_y + \rho \frac{\sigma_y}{\sigma_{BSA}} (BSA - \mu_{BSA})$$

$$SD(Y|BSA) = \sigma_y \sqrt{1 - \rho^2}$$

where ρ is the correlation between the echo measurement and BSA in each group, σ_y and σ_{BSA} are the group SDs of the echo measures and BSA respectively, and μ_{BSA} is the group mean BSA. These quantities can be estimated using each group's observed data.

The equations above are equivalent to fitting a linear regression model of the form

$$Y = \alpha + \beta(BSA)^n$$

The power n of BSA will be determined so that the transformed BSA and echo measurement will have approximately a linear relationship. For example, the diameters of the great vessels and the semilunar valve orifices have been found to relate most closely in a linear fashion to $BSA^{0.5}$ (9).

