Once the best available method for obtaining BSA has been determined and the simplest, best-fit model has been identified for each of the variables, the next step will involve examination for non-constant variance (heteroscedasticity) for each regression. In general, all of these relationships are anticipated to manifest heteroscedasticity characterized by a progressively but not necessarily linearly increasing variance with increasing BSA. Under these circumstances, the method described by Altman (33) provides a simple and adequate approach to generate a constant variance relationship. Although more complex methods (log or other transforms of one or both variables) have been described, they lack a physiologic basis and do not generally outperform the Altman technique. If there are individual variables for which the Altman methodology fails to adequately eliminate heteroscedasticity, the Lambda-Mu-Sigma method described by Cole and colleagues (34) will be adopted for those specific variables.

The Z-scores for each of the 36 study groups (based on age, gender, and race) will be compared using a t-test and adjusted for multiple comparisons. Groups which are not statistically different may be combined. For example, if the Z-scores for a particular measurement are not statistically different between males and females, the two groups may be combined and a new estimate of the mean and SD for the combined group will be determined.

The potential relationship of each set of Z-scores to height, weight, and BMI will also be examined using linear regression, and the potential for differences related to ethnicity will be examined using analysis of variance.

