6.2 Number of Subjects to be Enrolled

Sample size calculations were performed to determine the number of patients needed for each of the 36 study groups that will provide reasonable estimates of the population mean and SD for each measurement (35). There are several assumptions associated with these calculations:

- All variables should be normally distributed. Any variable that does not meet the normality assumption will need to undergo a mathematical transformation.
- At least 80% of the submitted echo studies will contain all the necessary images to perform each of the study measurements. In other words, for every group of 100 study patients, one would expect at least 80 studies in which each particular measurement can be made.

Assuming a normal distribution, a confidence interval for the SD is given by the following equation:

$$\sqrt{\frac{(n-1)s^2}{\chi_{n-1}^{2(1-\frac{\alpha}{2})}}} \leq \sigma \leq \sqrt{\frac{(n-1)s^2}{\chi_{n-1}^{2(\frac{\alpha}{2})}}}$$

We can minimize the width and solve for n such that

$$\sqrt{n-1} \left(\frac{1}{\sqrt{\chi_{n-1}^{2(\frac{\alpha}{2})}}} - \frac{1}{\sqrt{\chi_{n-1}^{2(1-\frac{\alpha}{2})}}} \right) < r$$

where r is some proportion of the observed point estimate of the SD. For $n = 80$ and $\alpha = 0.05$, the width of a 95% confidence interval would be 32% ($r = 0.32$) of the observed SD. In addition, the margin of error is calculated as

$$\frac{z_{\frac{\alpha}{2}} \sigma}{\sqrt{n}}$$

For $n = 80$, the margin of error for the mean would be 22% of the observed SD. Given the 80% echo quality assumption discussed above, each of the 36 study groups should have 100 patients in order to satisfy the requirements for the 95% confidence interval and margin of error for the mean. Thus the total sample size for the study is 3600 patients.

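### Sections 6.1 and 6.2 require normality of BSA and the raw measurements, but the Z-score needs it only of the residuals, which the protocol never checks

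*Protocol*

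**What the plan says.** Protocol section 6.1 starts the analysis with a distributional screen: "The distribution of BSA and each echo measurement will be assessed and tested for normality". What follows is mandatory: "Any variable found to be skewed or otherwise non-normal will be transformed appropriately in order to obtain a normal (or close to normal) distribution". The screen comes before subjects are classified into the 36 groups, and the text does not say whether it is pooled or run within groups.

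Section 6.2 carries the same rule into the sample size assumptions: "All variables should be normally distributed", and "Any variable that does not meet the normality assumption will need to undergo a mathematical transformation".

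Section 6.1.1 gives the conditional mean and SD of a measurement at a given BSA and adds: "The equations above are equivalent to fitting a linear regression model of the form". The regressor is BSA raised to a power, with its own criterion: "The power n of BSA will be determined so that the transformed BSA and echo measurement will have approximately a linear relationship".

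Section 6.1.2 then looks at non-constant variance and adopts the Altman method. Of log and other transforms of either variable it says that "they lack a physiologic basis and do not generally outperform the Altman technique". LMS is the fallback where the Altman method leaves heteroscedasticity. No section describes a normality check of residuals or of the resulting Z-scores.

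**The concern.** A Z-score places a child within the distribution of the measurement among children of the same BSA. Section 3.1 reads ±2 as cutting off 2.5% at each end. That holds if the measurement is normal given BSA, which means normal standardised residuals. BSA is a regressor and needs no particular distribution. Its shape here is set largely by filling six age bands from birth to 18 years. The raw measurement largely inherits that shape.

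A screen on the marginal distributions can therefore go wrong both ways. It can transform a measurement whose residuals were already normal, and it can pass one whose residuals are skewed. The ±2 limits are what users of the database will apply. Left ventricular volumes and mass, where the effect is largest, are among the outcomes listed in section 4.3.1.

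**Working it through.** **1. The plan's own figures (section 6.2, n = 80, α = 0.05).**
- Relative width of the 95% interval for the SD: √79 × (1/√56.31 − 1/√105.47) = 8.888 × (0.1333 − 0.0974) = 0.319. Stated: 32%.
- Margin of error for the mean: 1.96/√80 = 0.219 SD. Stated: 22%.
- 80/0.80 = 100 per group, and 36 × 100 = 3600.

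All reproduce. The chi-square interval for the SD does assume normality. In the model of section 6.1.1, the SD that enters the Z-score is σ_y√(1 − ρ²), the residual SD, so the assumption belongs to the residuals.

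**2. The sections side by side.**

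| Section | Applied to | Criterion | Action |
|---|---|---|---|
| 6.1, 6.2 | BSA and each measurement | marginal normality | transform |
| 6.1.1 | BSA | linearity with the measurement | choose power n |
| 6.1.2 | regression residuals | constant variance | Altman, then LMS |
| none | residuals or Z-scores | normality | none described |

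BSA has two transformation criteria and no stated precedence. The quantity that fixes the tails has no normality criterion.

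**3. Would the screen trigger?** The protocol gives no BSA distribution, residual CV or transformation family, so every input here is an assumption: mean BSA by age from 0.21 to 1.75 m², 10% scatter in BSA, six equal age strata, one sex and race stratum, and exactly normal residuals around c × BSA^p. Here p is 0.5 for diameters and 1.3 for volumes. The test is Shapiro-Wilk at 5%.
- Within an age group at n = 80, it rejects in 13–40% of draws for BSA, 3–10% for diameters and 16–66% for volumes. A second set of assumed growth curves gave 10–34% for BSA and 4–5% for the residuals.
- Pooled at n = 36 × 80 = 2880, it rejects BSA and the raw measurement in 100% of draws. Box-Cox does not cure this: the excess kurtosis of BSA goes only from about −1.3 to about −1.2.

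**4. Effect on the tails.** Same assumptions. Box-Cox is applied to both variables, followed by a per-group regression and the Altman SD. The comparator is the untransformed measurement on BSA^p with the same Altman step. Cut-points are ±1.96, so the target is 2.5% on each side.

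| Case | Below | Above |
|---|---|---|
| Untransformed + Altman, all cases | 2.4–2.6% | 2.4–2.6% |
| Diameters, CV 10–15%, pooled Box-Cox | 2.8–3.1% | 2.0–2.3% |
| Volumes, CV 15–20%, pooled Box-Cox | about 3.4–3.7% | 1.4–1.7% |
| Diameters, Box-Cox within age group | 2.5–3.1% | 2.0–2.5% |
| Volumes, Box-Cox within age group | 3.0–3.8% | 1.3–2.0% |

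The pooled Box-Cox power for volumes is about 0.3 (0.34 at CV 15%, 0.31 at CV 20%). A power below 1 applied to a conditionally normal measurement skews its residuals to the left, hence the heavier lower tail. Per 1000 normal children, a volume would be flagged high in 14–17 instead of 25, and low in 34–37 instead of 25.

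**The case against.** - **There is a reason for the rule.** The equations in section 6.1.1 have bivariate-normal form, for which near-normal variables are a customary working assumption. That explains the rule but does not rescue it. The protocol itself equates the equations with a linear regression, which needs no normal regressor, and normal marginals do not guarantee joint normality.
- **Residual checks are often left to the SAP.** True, and their absence alone would not be a finding. Here the protocol fixes a mandatory check on a different quantity.
- **A reader might infer a flat contradiction with section 6.1.2.** The text does not support that. The remark on transforms concerns variance stabilisation only, section 6.1.1 itself uses a power of BSA, and LMS is a power-transform method. The passages are unreconciled rather than opposed.
- **A reader might infer that the screen overrides the power n.** No section says so. The power BSA^n could be read as the transformation that section 6.1 has in mind.
- **A reader might infer that transformation is certain, from the 100% rejection rates.** Those rates need pooled testing, which the text does not specify. Within groups, BSA would pass the screen more often than not under these assumptions.
- **The harm is conditional and mostly small.** This stands. Of 28 direct measurements, 25 are diameters, lengths or thicknesses; volumes and mass are 4 of the 6 calculated quantities. The simulations transform in every case, use one family and assume normal residuals, so transforming the measurement could only do harm in them. The protocol would also accept a distribution that is close to normal.

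**Conclusion.** The point holds in a limited form. The normality rule in sections 6.1 and 6.2 is aimed at the marginal distributions, while the Z-score depends on the distribution given BSA, for which no normality check is described. This follows from the text and needs no simulation.

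The size of the effect does rest on assumptions: normal residuals, Box-Cox of both variables, and the assumed CVs. On those terms the distortion is modest for diameters and material for volumes, where the upper tail falls to roughly 56–68% of its target (1.4/2.5 to 1.7/2.5). It would be wrong to say that transformation always damages the limits. With right-skewed residuals, transforming the measurement could improve them, and the marginal screen cannot tell the two situations apart. The sample size of 3600 is not affected.

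**What to change.** - **Section 6.1:** remove the normality test and transformation of the marginal distributions of BSA and the measurements.
- **Section 6.1.1:** keep linearity as the sole criterion for the BSA power.
- **Section 6.1.2:** after the Altman SD step, assess the standardised residuals of each measurement for normality. Where they fail, use LMS, which the section already names; extend its trigger from residual heteroscedasticity to residual non-normality.
- **Section 6.2:** restate the normality assumption as applying to the measurement given BSA. Do not delete it, because the chi-square interval for the SD depends on it.

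The cost is a wording change in these sections and slight extra analysis work. No new data are needed and the sample size stays at 3600.

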6.1.1 Derivation of Mean and Standard Deviation

The mean and SD of a given measurement will be derived for each of the 36 study groups described above. For a given group, the mean (E) and SD of an echo measurement (Y), given the BSA, are as follows:

$$E(Y|BSA) = \mu_y + \rho \frac{\sigma_y}{\sigma_{BSA}} (BSA - \mu_{BSA})$$

$$SD(Y|BSA) = \sigma_y \sqrt{1 - \rho^2}$$

where ρ is the correlation between the echo measurement and BSA in each group, σ_y and σ_{BSA} are the group SDs of the echo measures and BSA respectively, and μ_{BSA} is the group mean BSA. These quantities can be estimated using each group's observed data.

The equations above are equivalent to fitting a linear regression model of the form

$$Y = \alpha + \beta(BSA)^n$$

The power n of BSA will be determined so that the transformed BSA and echo measurement will have approximately a linear relationship. For example, the diameters of the great vessels and the semilunar valve orifices have been found to relate most closely in a linear fashion to $BSA^{0.5}$ (9).

6.1.2 Analysis of Secondary Outcomes

A secondary analysis will determine whether another method of calculating BSA is superior to the Haycock formula for describing the relationship between BSA and the cardiovascular parameters. The published formulas in most common use are:

The formula of Du Bois and Du Bois (28):

$$BSA = 0.00718 \times \text{height}^{0.725} \times \text{weight}^{0.425}$$

The method of Dreyer and Ray (29):

$$BSA = 0.1 \times \text{weight}^{0.6666}$$

The two methods published by Boyd (30):

$$BSA = 0.0004688 \times (1000 \times \text{weight})^{0.8168} - 0.0154 \log(1000 \times \text{weight})$$

$$BSA = 0.0003207 \times (1000 \times \text{weight})^{0.7285} - 0.0188 \log(1000 \times \text{weight}) \times \text{height}^{0.3}$$

The formula of Haycock and colleagues (27):

$$BSA = 0.024265 \times \text{height}^{0.3964} \times \text{weight}^{0.5378}$$

The formula of Gehan and George (31) based on Boyd's data:

$$BSA = 0.02350 \times \text{height}^{0.42246} \times \text{weight}^{0.51456}$$

The formula of Mosteller (32):

$$BSA = ((\text{height} \times \text{weight})/3600)^{0.5}$$

The data will be divided into two groups, 30% for training and 70% for testing. The training dataset will be used to determine the best method for calculating BSA, and the remaining data will be used to validate the results. For each regression using the training dataset, the coefficient of determination will be derived for each method of calculating BSA, and the method demonstrating the highest mean coefficient of determination for all variables will be selected as the optimal BSA calculation method. Alternate approaches to identify the optimal BSA calculation method will be considered and will include likelihood-based comparisons of model fit (such as the Aikake or the Bayesian information criteria). In addition, other cross-validation techniques using different sizes for the training and testing datasets or the jackknife (or “leave one out”) procedure will also be utilized. If these analyses reveal a better method for calculating BSA than the Haycock formula, then the primary analysis to determine the relationship between the individual echo measurements and BSA will be performed again, this time using the BSA derived from the best method.

Once the best available method for obtaining BSA has been determined and the simplest, best-fit model has been identified for each of the variables, the next step will involve examination for non-constant variance (heteroscedasticity) for each regression. In general, all of these relationships are anticipated to manifest heteroscedasticity characterized by a progressively but not necessarily linearly increasing variance with increasing BSA. Under these circumstances, the method described by Altman (33) provides a simple and adequate approach to generate a constant variance relationship. Although more complex methods (log or other transforms of one or both variables) have been described, they lack a physiologic basis and do not generally outperform the Altman technique. If there are individual variables for which the Altman methodology fails to adequately eliminate heteroscedasticity, the Lambda-Mu-Sigma method described by Cole and colleagues (34) will be adopted for those specific variables.

The Z-scores for each of the 36 study groups (based on age, gender, and race) will be compared using a t-test and adjusted for multiple comparisons. Groups which are not statistically different may be combined. For example, if the Z-scores for a particular measurement are not statistically different between males and females, the two groups may be combined and a new estimate of the mean and SD for the combined group will be determined.

The potential relationship of each set of Z-scores to height, weight, and BMI will also be examined using linear regression, and the potential for differences related to ethnicity will be examined using analysis of variance.

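### The stated rule chooses the BSA formula on 30% of the children, so the answer to secondary aim 1 is noisier than it need be; a resampling analysis over all children should decide

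*Protocol*

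**What the plan says.** Secondary aim 1 (Protocol section 2.2) is to find the BSA formula that best describes how cardiovascular structures scale with body size. Section 6.1.2 lists seven published formulas and then sets the procedure:

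- The split: "The data will be divided into two groups, 30% for training and 70% for testing".
- The role of each part: "The training dataset will be used to determine the best method for calculating BSA, and the remaining data will be used to validate the results".
- The rule, applied to the training-set regressions: "the method demonstrating the highest mean coefficient of determination for all variables will be selected as the optimal BSA calculation method".
- Likelihood criteria: "Alternate approaches to identify the optimal BSA calculation method will be considered and will include likelihood-based comparisons of model fit".
- Further resampling, which the section commits to using in addition: "other cross-validation techniques using different sizes for the training and testing datasets or the jackknife" (that is, leave-one-out).

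If these analyses together show a formula better than Haycock, the primary analysis is run again with it. The section does not rank the analyses and gives no criterion for what counts as validated on the 70%.

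**The concern.** A large hold-out is useful when candidates can overfit to different degrees. Here they hardly can. The coefficients of all seven formulas are published constants, and each formula enters the same regression form (section 6.1.1: an intercept, a slope and a power of BSA). The number of quantities fitted per measurement is the same for every candidate.

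What limits the comparison is precision. Haycock, Gehan-George and Mosteller have similar exponents, so their R-squared values lie very close together and sampling noise largely decides which comes first. The written rule gives the smaller part of the data to the step that makes the choice, and the larger part to a check that needs much less.

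At stake is how reliable the answer to secondary aim 1 is. The choice can also replace Haycock in the primary analysis.

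**Working it through.** **Inputs from the Protocol.** Section 6.2: "Thus the total sample size for the study is 3600 patients", in 36 groups of 100, with at least 80% of studies measurable for each measurement. Section 6.1.2: the 30/70 split and the selection rule. Section 4.3.1: 28 measurements and 6 calculated variables.

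**The plan's own figures.** These reproduce. For n = 80 the 95% interval for the SD has width 0.319 of the SD (stated 32%). The margin for the mean is 1.96/sqrt(80) = 0.219 (stated 22%). 80/0.8 = 100 per group, and 36 x 100 = 3600. The Protocol gives no precision figure for the comparison of BSA formulas.

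**Children available for the choice.** 0.30 x 3600 = 1080. With 80% measurable, 0.80 x 1080 = 864 out of 0.80 x 3600 = 2880, or 24 of 80 per group.

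**Noise.** The standard error of an R-squared difference scales as 1/sqrt(n).
- 30% against all children: sqrt(1/0.30) = 1.83.
- 30% against a 70% training part: sqrt(0.70/0.30) = 1.53.

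**Choice between two formulas.** If the better formula wins with probability Phi(z) on all data, it wins with probability Phi(z x sqrt(0.30)) on 30%. So 90% becomes 76%, 95% becomes 82%, and 99% becomes 90%.

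**Choice among all seven, by simulation.** The following are assumptions, not Protocol figures: growth curves for 36 x 100 children; 28 measurements, each 80% measurable; residual CV of 6%, 10% or 15% (1.6 times that for areas); residual correlation 0.3; one listed formula true. One regression per measurement was fitted over all groups, and the formula with the highest mean R-squared was chosen. There were 150 runs, with Monte Carlo error of about 4 points. Chance of choosing the true formula:

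| True formula | CV | 30% | 70% | All |
|---|---|---|---|---|
| Haycock | 6% | 72% | 81% | 86% |
| Haycock | 10% | 48% | 67% | 71% |
| Haycock | 15% | 40% | 56% | 57% |
| Mosteller | 10% | 53% | 76% | 83% |
| Gehan-George | 10% | 30% | 49% | 57% |
| Du Bois | 10% | 97% | 100% | 100% |
| Du Bois | 15% | 83% | 95% | 97% |

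From all children to 30%, the loss before rounding is 14 to 31 points in the first five rows. It is 3 and 15 points in the two Du Bois rows. The simulated SD of the R-squared difference was mostly 1.6 to 2.0 times larger on 30%, in line with 1.83. With separate regressions in the 36 groups (60 runs), the ratio was about 1.3 to 1.8 and the loss 8 to 22 points.

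A second simulation used 34 variables with means proportional to BSA^0.5, CV 10% and residual correlation 0.1 to 0.5. On 30% / 70% / all children it gave Haycock 42-69 / 55-82 / 63-86%, Mosteller 41-70 / 60-82 / 65-91%, Gehan-George 18-40 / 32-62 / 41-72% and Du Bois 83-99 / 93-99.7 / 96-100%.

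**Cost of a wrong choice.** The average R-squared lost by choosing on 30% was below 0.0001 with pooled regressions and at most about 0.0003 within groups. In a separate check (2880 children, mean proportional to BSA^0.5, CV 10%), swapping among Haycock, Gehan-George and Mosteller moved a Z-score by 0.005 to 0.022 on average, with a 99th percentile of at most about 0.07.

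**The case against.** The strongest reply is that the same paragraph already supplies the remedy. Other split sizes or leave-one-out are a commitment, leave-one-out uses nearly every child, and the trigger for rerunning the primary analysis refers to the analyses in the plural. This stands. A reader might infer that the formula is chosen on 30% of the data and nothing else; the text does not support that. What remains is that the only method the section says will be selected as optimal is the training-set winner, while the other analyses are added beside it without a statement of which one governs. A statistical analysis plan, not available here, could settle that order. The 30% rule itself is written in the Protocol.

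A reader might also infer that 70% of the information is thrown away. It is not: it serves as an independent check. That check has some value, and out-of-fold results that have picked the winner no longer validate it independently.

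A third tempting inference is that the Z-scores would be materially wrong. Nothing supports this. The larger losses in the table arise where formulas are almost interchangeable, and Z-score shifts of about 0.02 are small beside the 22% of an SD that section 6.2 accepts as the margin for a group mean.

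Finally, the simulated percentages depend on quantities the Protocol does not give. Section 6.1.1 offers BSA^0.5 only as an example for great vessels and semilunar valves, so using it for all 34 variables is a simplification. Even with all children, Gehan-George is identified only 41 to 72% of the time in the second simulation, so much of the difficulty is near-equivalence and not the split.

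**Conclusion.** The point holds as a matter of efficiency for secondary aim 1, at low severity. The stated selector uses the smaller part of the data in a setting where a large hold-out protects against little. The noise factors of 1.83 (against all children) and 1.53 (against a reversed split) follow from the split fractions alone. The loss in the chance of naming the true formula depends on the assumed growth curves, CVs and residual correlations and on which formula is true: roughly 15 to 30 points among the near-equivalent formulas, and about 3 to 15 points when Du Bois is true. The additional resampling mitigates this in part, but it is not made decisive. The consequence is a less reliable answer to a stated aim, not a demonstrable error in the reference values.

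**What to change.** In section 6.1.2, name one deciding analysis: leave-one-out or repeated k-fold cross-validation over all children, choosing the formula with the best mean out-of-fold fit across variables. Report the 30/70 result, other split sizes and the likelihood criteria as sensitivity checks, and state that they do not override the deciding analysis. If a single split must remain the selector, reverse it to 70% training and 30% testing.

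The cost is a few sentences and some computing time; no further children are needed. The downside is the loss of a single untouched hold-out set, or a smaller one if the split is reversed. With fixed candidate formulas that differ little in overfitting, that is a small price.

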3. BACKGROUND INFORMATION

3.1 Background

Echocardiography is crucial for the evaluation of children with congenital and acquired heart diseases. It is the primary imaging modality for establishing diagnoses, determining treatment options, monitoring disease progression, and assessing the effects of intervention. The sizes of cardiovascular structures are frequently affected by the abnormal hemodynamics of a disease state, particularly in children. Because treatment decisions rely on an accurate determination of cardiovascular size, quantification is an important component of the echo study (1, 2). Reliable, accurate, and generalizable normal reference values must be readily available for clinicians to distinguish a normal finding from an abnormal one and to determine if the size of a structure is adequate, too small, or too large to function effectively. In addition to their importance in the clinical setting, reference values are also used to define the population of interest and as primary or secondary outcomes in research studies designed to evaluate medical or surgical therapies (3-5).

Previous studies suggest that measurements in normal children are confounded by body size, age, gender, and race (6-11). Adjustments must be made for these factors before the effect of a disease state on the cardiovascular system can be assessed. Echo Z-scores have gained widespread acceptance in both clinical practice and research in pediatric cardiology (9, 12-18). Similar to growth charts, they allow comparisons of cardiac measurements obtained for an individual child with measurements obtained from a normal population adjusted for the effects of body size, age, gender, and/or race. The Z-score corresponding to a particular observation in a dataset is defined as

$$Z = \frac{\text{observation} - \text{mean}}{\text{standard deviation}}$$

The Z-score tells us how many SDs the observation is from the mean, and it is positive or negative according to whether the observation lies above or below the mean. It can be calculated from various subpopulations based on a particular set of parameters (including body size, age, gender, and race). For example, a Z-score of +2 (or -2) for a given population corresponds to a measurement that is two SDs above (or below) the expected mean,

corresponding to the 95% confidence interval where 2.5% of the population is expected to have values above and 2.5% below this interval.

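### As Section 6.1.1 defines them, the Z-scores t-tested in Section 6.1.2 have mean zero in every study group, so the only stated criterion for merging groups is uninformative

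*Protocol*

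**What the plan says.** Protocol Section 6.1.1 sets the level of estimation: "The mean and SD of a given measurement will be derived for each of the 36 study groups described above". The inputs to its formulas for E(Y|BSA) and SD(Y|BSA) are group quantities. For example, rho "is the correlation between the echo measurement and BSA in each group", and the means and SDs also come from the group's own data. The section adds: "The equations above are equivalent to fitting a linear regression model of the form" Y = alpha + beta(BSA)^n, which contains an intercept.

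Section 3.1 defines Z as the observation minus the mean, divided by the SD, and allows the mean and SD to come from a subpopulation.

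Section 6.1.2 chooses a BSA formula, settles a model for each measurement and deals with non-constant variance by Altman's method, or by LMS where that fails. It then compares the groups: "The Z-scores for each of the 36 study groups (based on age, gender, and race) will be compared using a t-test", with adjustment for multiple comparisons. The decision rule is: "Groups which are not statistically different may be combined". For males and females who do not differ, "the two groups may be combined and a new estimate of the mean and SD for the combined group will be determined". Section 6.3 confirms that multiplicity is controlled for this collapsing step.

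**The concern.** A comparison of groups is informative only if all groups are measured against the same yardstick. If each child's Z-score is taken from the regression of that child's own group, any difference between groups has been removed before the test is run. Lack of significance is then guaranteed and says nothing about whether the groups are alike.

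This t-test is the only criterion the protocol gives for keeping groups apart or merging them. The primary aim is reference values adjusted for body size, age, gender and race. Section 3.2 counts missing adjustment for gender and race among the faults of existing databases, and Section 10 says the study can determine differences between Whites and African-Americans. A merging step that cannot see a difference gives no basis for simplifying the adjustment.

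**Working it through.** **The plan's own figures.** Section 6.2 uses 80 measurable studies per group.
- Width of the 95% interval for the SD: sqrt(79) × (1/sqrt(chi-square 0.025, 79 df) − 1/sqrt(chi-square 0.975, 79 df)) = 0.319 (stated 0.32).
- Margin of error for the mean: 1.96/sqrt(80) = 0.219 SD (stated 22%).
- 80/0.80 = 100 per group; 6 × 2 × 3 = 36 groups; 36 × 100 = 3600.

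All reproduce. The checks below use n = 80 per group.

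**Algebra.** Average Y − E(Y|BSA) over one group, using the Section 6.1.1 formula:

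(group mean of Y − mu_y) − rho × (sigma_y/sigma_BSA) × (group mean of BSA − mu_BSA).

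Because mu_y and mu_BSA are estimated by that group's own means, both brackets are 0. Dividing by the group SD leaves 0. The same holds with BSA^n in place of BSA. For any two groups the difference in mean Z is 0 − 0, so t = 0 and p = 1 whatever the true difference.

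**Simulation.** Assumptions: two groups of 80, BSA normal with SD 0.15, Y linear in BSA, residual SD 1, two-sided 0.05 (the protocol does not state sidedness), 2000 runs, no multiplicity adjustment. The common-reference column fits one BSA regression to both groups, which have equal BSA distributions.

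| True shift (residual SDs) | Own-group Z-scores: rejected | Common-reference Z-scores: rejected |
|---|---|---|
| 0 | 0% | 5.1% |
| 0.25 | 0% | 34.7% |
| 0.5 | 0% | 87.3% |
| 1 | 0% | 100% |
| 2 | 0% | 100% |
| 5 | 0% | 100% |

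The largest |t| with own-group Z-scores was about 2e-13, which is rounding error. The usual formula, Phi(d × sqrt(80/2) − 1.96), agrees with the last column: Phi(1.581 − 1.96) = 35% at 0.25 SD and Phi(3.162 − 1.96) = 89% at 0.5 SD.

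**Variations.**
- Slope 20% steeper and SD doubled in one group, with a 1 SD shift: own-group Z-scores, 0% rejected.
- SD modelled from absolute residuals in the Altman manner, 1 SD shift: mean Z is only approximately zero, largest |t| 0.20, still 0% rejected. The data simulated here had constant variance. LMS was not simulated.
- SD doubled, no shift in mean: 0% with own-group Z-scores and 4.7% with common-reference Z-scores. A t-test of means does not see a difference in SD on either basis, although a Z-score depends on the SD as much as on the mean.

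**Would a common BSA-only reference be enough?** Set mean BSA 0.6 apart (0.6/0.15 = 4 SDs), as a stand-in for age groups with little overlap. The t-test on common-reference Z-scores then rejected in 0.15% of runs at a 0.5 SD shift and 5.05% at a 1 SD shift. The BSA slope absorbs the shift: the mean difference in Z at a true 1 SD shift was 0.19, against 0.89 when the BSA distributions coincide.

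A group term fitted jointly with BSA (common slope) keeps the information. Its variance is 1/80 + 1/80 + 0.6²/(2 × 80 × 0.15²) = 0.025 + 0.36/3.6 = 0.125, so SE = 0.354. Power at a 1 SD shift is Phi(1/0.354 − 1.96) = Phi(0.87) = 81%. Simulation of the same case also gave 81%, with 4.9% rejection at no shift.

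**The case against.** **The Z-scores may come from one model per measurement.** Section 6.1.2 chooses the BSA formula on a split of the data without mentioning groups, settles a model for each measurement, and expects variance to rise with BSA. That fits a regression over the whole paediatric range better than one within the youngest age group. On this reading the comparison is meaningful. The reading is possible, but the protocol never states a common reference, and Section 6.1.1 makes every parameter group-specific. It also does not rescue the test across age groups, as the 4 SD case shows.

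**The re-estimation wording proves nothing.** A reader might take the promise that "a new estimate of the mean and SD for the combined group will be determined" as proof that the Z-scores before merging are group-specific. It is not. Section 6.1.1 already yields a mean and SD per group, and these would need re-estimation after a merge whichever model supplied the compared Z-scores. The finding rests on Section 6.1.1 and the absence of any stated alternative.

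**The zero is not always exact.** This is correct. It is exact for the least-squares formulas and approximate after Altman scaling. The practical result was the same under Altman scaling; LMS is unchecked.

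**The primary estimates survive.** This is also correct. Merging is permitted, not required; Section 6.1.1 delivers all 36 group estimates without a test; and the sample size rests on their precision. A p-value of about 1 for every pair would also be noticed, and Section 6.5 provides for a documented revision.

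**A separate SAP may settle it.** The protocol itself fixes the test, its input and the merging rule, so this is a stated rule that fails, not a detail left open.

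**Conclusion.** The concern holds on the plain reading of Sections 6.1.1 and 6.1.2. The t-test compares quantities whose group means are zero by construction, or close to it after Altman scaling. It rejected in 0 of 2000 runs at every shift tried up to 5 residual SDs, where Z-scores from a common reference rejected in 87.3% of runs at 0.5 SD when BSA distributions coincide. Every pair of groups would qualify for merging, and the multiplicity adjustment cannot change a p-value that is already about 1.

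The conclusion assumes that the compared Z-scores come from the Section 6.1.1 regressions, the only source the protocol states. The size of the contrast depends on the simulated BSA distributions; the zero itself does not.

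A reader might infer that the primary product must collapse to Z-scores adjusted for BSA alone. The protocol does not support that, because merging is optional and the 36 group estimates stand. What fails is the only stated criterion for keeping or dropping the age, gender and race adjustment. Since it bears on the final form of the reference values, it should be corrected before the analysis.

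**What to change.** Replace the t-test paragraph in Section 6.1.2. For each measurement, fit one joint model to all subjects in BSA^n with the chosen variance function, and include age, gender and race terms on the intercept, the slope and the residual SD. Decide on merging by nested F or likelihood-ratio tests of those terms, using the multiplicity adjustment already planned in Section 6.3. The terms on the residual SD are needed because a comparison of means does not detect a difference in spread.

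Do not rely on Z-scores from a common BSA-only reference as a sufficient alternative: where age groups differ strongly in BSA, the reference absorbs much of the difference being tested.

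The cost is one reworded paragraph and slightly more modelling. No new data are needed, and the sample size in Section 6.2 does not change.
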